## LIST OF ABBREVIATIONS

AE	Adverse Event
AMC	Academic Medical Center
APH	Antepartum hemorrhage
AR	Adverse Reaction
CUAMM	Doctors with Africa – CUAMM
EC	Ethical Committee
GCP	Good Clinical Practice
IC	Informed Consent
ICU	Intensive Care Unit
PCMH	Princess Christian Maternity Hospital
(S)AE	(Serious) Adverse Event
US	Ultra Sound
POCUS	Point-of-care Ultra Sound

## 1. PROJECT SUMMARY

**Rationale:** The majority of obstetric emergencies are identified through clinical examination, which cannot be substituted by ultrasound. However, just as a laboratory exam, ultrasonography can provide swift point of care information on fetus presentation, viability, placenta position, quantity of amniotic fluid and presence of abdominal fluid to inform the clinical reasoning and therapeutic escalation. Ultrasound literature in low-resource settings has favoured antenatal care (ANC) rather than the emergency setting. Also, hand-held ultrasound machines may not be as performant as traditional machines used by expert operators but to date is still to be tested in a low resource setting.

**Objective:** to assess the *reliability* of **ultrasound findings** measured by hand held ultrasound probes used by operators with variable experience in a low resource hospital.

**Hypothesis:** There is substantial agreement between simple ultrasound findings identified using hand held ultrasound devices and the reference standard.

**Study design:** a prospective observational diagnostic accuracy study.

**Study population:** parturients admitted to the Princess Christian Maternity Hospital (PCMH) in Freetown, Sierra Leone.

**Sample size:** no formal sample size calculation is performed. Based on current rates of admissions to the PCMH we expect to perform obstetrical ultrasound scan in at least 300 patients during a 2–months study period.

**Methods:** 4 trained physicians (3 naive and 1 intermediate ultrasound users) will perform the ultrasound investigations using the hand held device and complete a structured predefined report form of obstetric ultrasound findings at patient admission or according to clinical indications after admission. These will be compared with the reference standard, i.e. an ultrasound examination performed by a specialist gynecologist/obstetrician using a conventional apparatus in the hospital ultrasound room.

**Main study parameters/primary endpoints:** The mean diagnostic accuracy among nine ultrasound obstetric findings collected with hand held devices versus the reference standard.

**Nature and extent of the burden and risks associated with participation, benefit and group relatedness:** Ultrasound is a non–invasive and painless procedure without additional risks.

## **2. INSTITUTIONS INVOLVED IN THE PROJECT**

### **2.1.Princess Christian Maternity Hospital**

The Princess Christian Maternity Hospital (PCMH) in Freetown, Sierra Leone, is a maternity referral hospital and the only one qualified for comprehensive emergency obstetric care in the whole Western Area. The theoretical reference population amounts to 1.5 million inhabitants. PCMH is by constitution a primarily obstetric institution, with approximately 9,000 admissions per year, including 6,000 deliveries (of which 30% by cesarean section). Approximately one-third develop major obstetric emergencies, including peripartum hemorrhage, sepsis and pre-eclampsia. The PCMH has 149 beds in 7 wards. The theatre facilities are essential, anesthetic service is present with a majority of spinal anesthesia procedures. PCMH recently opened an 8-bed high-dependency unit (HDU) focusing on care for critically ill parturients.

### **2.2.Doctors with Africa CUAMM**

'Doctors with Africa – CUAMM' (CUAMM) is an Italian non-governmental organization, which has been supporting health service delivery in Africa for over 60 years. Currently, it is active in 7 African countries. Its main focus is maternal, newborn and child health at a district level. CUAMM activities in PCMH started in 2016, focusing on strengthening of clinical and management activities.

## **3. BACKGROUND AND JUSTIFICATION**

### **3.1.Ultrasound implementation in low and middle income countries**

Ultrasound examinations in obstetric have been indispensable in high-income countries for many years. However, it has been shown recently that its use for antenatal visits in low- and middle-income countries (LMICs) did not necessarily mean improvements in perinatal outcomes. In fact the use of ultrasound did not improve maternal and neonatal mortality based on the results of a large cluster-randomized control trial in five LMICs (1). Furthermore, they found that there was no significant improvement in attendance rates of antenatal care of pregnant women, thus suggesting that resources should not be used for the introduction of ultrasound practices in resource limited settings.

Unexpected severe findings such as multiple pregnancy, breech presentation, or intra uterine fetal demise at the time of delivery are commonly found (2). These complications often resulted in high morbidity and mortality of pregnant women and newborn babies. As it may take long to improve capacity to screen out high-risk pregnancies at antenatal contacts, enhancing diagnostic and treatment capacity of the tertiary hospital to cope with these unexpected conditions will currently be most required.

### **3.2. Point of care and hand held ultrasonography**

Point-of-care ultrasonography (POCUS) has recently been recognized as a powerful tool to support bedside clinical diagnosis mostly in emergency settings. As technology advances, ultrasound devices became more compact to the point of being hand carried also by physicians not specialized in ultrasound. Their use in resource-limited settings has been studied in emergency departments in tertiary care hospitals in Rwanda and Tanzania with substantial impact on clinical decision making processes (3,4).

Hand held ultrasound devices usually have a low frequency probe (2-5 MHz) with a smart phone or tablet functioning as an interface. The interface of the device is designed to handle simple functions as freeze, zoom, basic measurements and gray-scale adjustment. It can also perform obstetric calculations e.g. for estimation of gestational ages based on the measurements of bi-parietal diameter (BPD) or femur length (FL).

### **3.3. Feasibility issues with POCUS**

Feasibility of POCUS in obstetric emergencies has also been studied mostly in high-income countries and shown to be useful for physicians not specialized in obstetrics to identify normal pregnancy and identify differential diagnoses for parturients who present at the emergency department with acute symptoms (6-10). Application of POCUS in antenatal settings has been studied in Kenya where a trained midwife successfully conducted screening of high-risk pregnancies (5). However, there is paucity of information of POCUS obstetric application in resource limited settings especially to manage emergency cases and detect simple but important obstetric findings.

### **3.4. Current challenges with obstetric diagnostics in PCMH**

Princess Christian Maternal Hospital (PCMH) is only the tertiary perinatal hospital in Freetown, Sierra Leone, which accommodates nearly 9000 admissions a year (11). More than 6000 deliveries a year are managed at the hospital, with more than one third of cases being major obstetrical emergencies including eclampsia and peripartum hemorrhages. Furthermore, the hospital accepts emergency referrals from 6 hospitals and 112 peripheral clinics in the Western region of the country. Major causes of maternal mortality at PCMH include postpartum and antepartum hemorrhage, eclampsia and infection (12).

In the 2017 Annual Report (12), it was shown that diagnoses made at admission by house doctors at outpatient department were frequently different from the final diagnoses made by the house officers specialized in obstetrics. For example, approximately 40% of the patients admitted to the hospital were initially diagnosed with anemia, but most of them were subsequently found to be in fatal conditions caused by placenta abruption (12). It is obvious that confirming a diagnosis is not the

only step needed to avoid mortality, but it is pivotal to establish a functional system to save critically ill patients. Lack of access to ultrasound in the delivery room often resulted in late diagnosis of malpresentation, breech presentation or multiple pregnancies. Intra-uterine fetal death (IUFD) was frequently observed but unnoticed until they were delivered by unnecessary cesarean sections.

At the emergency outpatient department of PCMH, clinical examinations and history taking are the only means to reach diagnoses, based on which subsequent management strategies are planned. Measurement of hemoglobin and lactate are the only modality available for in-house doctors to support their diagnosis. Ultrasound machine is intermittently available but the frequent low quality of the images acquired and the unstable electric supply of the hospital hampers repeatability and reliability of the ultrasound examinations.

Stethoscope or doppler devices are seldom available or functional. Traube's monaural stethoscope is the only the device available for the in-house doctors or midwives to listen to the fetal heart. Prompt diagnosis and treatment decisions are frequently required in the case of obstetric emergencies, in which delay in the recognition of the conditions of the fetus and mothers often resulted in demise of both.

### **3.5. The present project**

Despite its clear operator dependency (13) and potential usefulness in the decision making process, feasibility and accuracy of portable ultrasound devices in obstetrics has been scarcely investigated. The objective of the study is to evaluate the reliability of simple pre-specified ultrasound findings acquired at the bedside with a hand-held apparatus with regards to five clinical scenarios most commonly encountered in the hospital, i.e. vaginal bleeding in early pregnancy, pre-eclampsia, prolonged/obstructed labor, antepartum hemorrhage (APH) and high risk pregnancies encountered in ANC. These will be compared to a reference standard, constituted by a conventional ultrasound examination performed by an expert gynecologist with a standard apparatus in the hospital dedicated scanning room.

## **4. STUDY GOAL AND OBJECTIVES**

### **4.1. Objectives**

#### **4.1.1. Primary Objective**

To determine the composite reliability of simple obstetric ultrasound findings collected by hand held ultrasound devices in a busy urban low resource setting.

#### **4.1.2. Secondary Objectives**

1. To assess the reliability for each pre-defined ultrasound finding.
2. To ascertain if the reliability varies between naïve and intermediate operators.

3. To establish the feasibility of examinations and quality of images acquired with the hand held apparatus.

#### **4.1.3.Primary Hypothesis**

There is substantial composite agreement between simple ultrasound findings identified using hand held ultrasound devices and the reference standard.

#### **4.1.4.Secondary hypothesis**

1. The diagnostic accuracy will be significantly higher for specific 'easier to detect' *individual ultrasound findings* such as intrauterine pregnancy, amniotic fluid estimation, cephalic presentation, and presence of abdominal fluid.
2. The diagnostic performance of the ultrasound *naïve operator* is significantly different from the intermediate operator only for more complex ultrasound findings such as fetal heart, presence of retroplacental hematoma, placenta location, estimation of gestational age and detection of multiple pregnancy.
3. The proportion of complete examinations is >90% and quality of images as estimated by a simple visual scoring system is high (more or equal to 3).

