## **5.2. Sample size calculation**

Sufficient information to perform a formal sample size calculation is lacking. During a 2-month period all patients meeting the inclusion and exclusion criteria will be recruited. Based on current rates of admissions in the mentioned services, we expect to recruit at least 300 patients (75 patients per operator, 15 for each of the 5 inclusion categories) during a 2 months data collection period.

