## **7.2. Statistical analysis**

Data will be reported as mean and standard deviation or median with interquartile range (continuous data), and as frequency and percentage (categorical data). The agreement between the hand-held device and the conventional apparatus on categorical findings scoring will be assessed using diagnostic accuracy and Cohen's K statistics. When appropriate, comparison between subgroups will be performed using Student's t test, ANOVA, Mann-Whitney test or Kruskal-Wallis test for continuous data, and with Chi-square test or Fisher's test for categorical data. A p-value less than 0.05 will be considered statistically significant. Statistical analyses will be performed using R (R Foundation for Statistical Computing, Vienna, Austria). The sensitivity, specificity, positive predictive value, and negative predictive value for each dichotomous ultrasound finding acquired with hand held devices against the reference diagnoses with conventional apparatus will be assessed when appropriate. Quality of images will be assessed by standardized scoring system from 0 to 4 (0= no meaningful images; 1 = poor, not sufficient for interpretation; 2 = good, acceptable for interpretation; 3= excellent, minor suggestions for interpretations; 4 = outstanding, no suggestions for interpretations). All analyses will be conducted after the end of patient recruitment and no interim analyses are planned.

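### Secondary hypothesis 2 makes a significance claim about operator experience from a single intermediate operator, and its wording lets non-significance count as no difference

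*Protocol*

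**What the plan says.** The Project Summary (section 1, Methods) fixes the operators: "4 trained physicians (3 naive and 1 intermediate ultrasound users". Secondary objective 2 (section 4.1.2) begins "To ascertain if the reliability varies between" and names the naïve and intermediate groups. Secondary hypothesis 2 (section 4.1.4) says that the naïve operator's performance "is significantly different from the intermediate operator only for more complex ultrasound findings such as fetal heart"; its list of complex findings goes on to retroplacental hematoma, placenta location, gestational age and multiple pregnancy. Hypothesis 1 in the same section gives the easier findings: "intrauterine pregnancy, amniotic fluid estimation, cephalic presentation, and presence of abdominal fluid".

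Section 5.2 states "Sufficient information to perform a formal sample size calculation is lacking" and expects "at least 300 patients (75 patients per operator, 15 for each of the 5 inclusion categories". For subgroup comparisons, section 7.2 offers a general list that includes "Chi-square test or Fisher's test for categorical data", with significance at p below 0.05. It names neither the unit of analysis nor an operator term. No equivalence margin appears anywhere. Section 6.1.4 says that there is no randomisation, and no rule for assigning women to operators is given.

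**The concern.** Two separate problems meet in hypothesis 2.

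First, with one intermediate operator, any difference between the levels is also a difference between one doctor and three others. A significant result would look like an effect of experience when it may reflect only that person's skill, or the women that person happened to scan. Because the operator count is fixed in the protocol, a separate SAP could not repair this.

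Second, the hypothesis predicts a significant difference for complex findings and for no others. For the easier findings the prediction is therefore met whenever the test is not significant. With few scans and no margin, that outcome is likely whether or not the operators differ.

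At stake is the study's answer on who can use the device reliably.

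**Working it through.** **Plan's own figure.** 4 operators × 5 categories × 15 women = 4 × 75 = 300. The figure in section 5.2 reproduces. No power is stated, so there is none to check.

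**Scans per finding.** Counting the categories in Table 2 that call for each finding and multiplying by 15 gives the intermediate operator's scans; three times that gives the naïve total.

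| Finding | Label in 4.1.4 | Categories | Intermediate vs naïve |
|---|---|---|---|
| Intrauterine pregnancy | easier | 1 | 15 vs 45 |
| Free fluid | easier | 1 | 15 vs 45 |
| Cephalic presentation | easier | 3 | 45 vs 135 |
| Amniotic fluid | easier | 4 | 60 vs 180 |
| Retroplacental hematoma | complex | 1 | 15 vs 45 |
| Placenta, gestational age, multiple pregnancy | complex | 2 each | 30 vs 90 each |
| Fetal heart | complex | 5 | 75 vs 225 |

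**Error rate if scans are the unit.** Simulation with no experience effect. Each of the four operators has logit accuracy = log(0.85/0.15) + SD × a standard normal draw. Scans are binomial given the operator, and a pooled chi-square compares 1 operator with 3 at two-sided 5%. The SDs and the 85% are assumptions.

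| Operator SD (logit) | Accuracy at ±1 SD | 15 scans per operator | 75 scans per operator |
|---|---|---|---|
| 0 | 85% | about 5% | about 5% |
| 0.2 | about 82-87% | about 6% | about 10% |
| 0.3 | about 81-88% | about 7% | about 15% |
| 0.5 | about 78-90% | about 10% | about 28% |

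More scans by the same operators make this worse: at SD 0.5, 300 scans per operator give about 55%.

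**Operators as the unit.** One against three leaves 2 degrees of freedom, t = 4.30. The 95% half-width is 4.30 × √(1 + 1/3) = 4.97 between-operator SDs, and that assumes that the intermediate level varies as much as the naïve level, which one person cannot show. This analysis is too imprecise to be useful.

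**Power for the easier findings.** Exact enumeration, ignoring operator variation, with the intermediate operator at 95%:

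| Finding | Fisher, naïve 85% | Fisher, naïve 80% |
|---|---|---|
| Intrauterine pregnancy, free fluid | 1.5% each | 9% each |
| Cephalic presentation | 41% | 71% |
| Amniotic fluid | 55% | 85% |

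At 15 vs 45, chi-square gives about 6% and 20% for the same two gaps. If all four easier findings truly differed by 10 points, the chance that none is significant under Fisher is 0.985 × 0.985 × 0.593 × 0.453 = 0.26, treating findings as independent.

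**What a no-difference claim would need.** Assume 90% accuracy in both groups, a 10-point margin, one-sided 2.5% and 80% power. The intermediate operator then needs (1.96 + 0.84)² × 0.09 × (1 + 1/3) / 0.10² ≈ 95 scans per finding, for one bound only and with operator variation ignored. The plan yields 15 to 75. At 15 vs 45 and 90% accuracy, the 95% half-width of the difference is 1.96 × √(0.09/15 + 0.09/45) = 0.175, or 17.5 points.

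**The case against.** Several points on the other side stand.

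- **It is secondary.** This is one of three secondary hypotheses in an observational study without a formal sample size. The primary endpoint does not use the contrast, so the point does not threaten the main result.
- **The scan-level test is inferred.** Section 7.2 is a general list and does not assign a test to hypothesis 2. An SAP could name the unit. This makes the error-rate figures conditional; the confounding remains. The endpoint on operators in section 6.1.2 is inter-observer agreement, but section 6.3.2 gives each woman one hand-held scan before the expert scan, so no paired naïve and intermediate readings are planned for it.
- **The protocol never says that it will report p>0.05 as equality.** A reader might infer such a rule; the text supports less. The wording allows non-significance to count as support, and nothing guards against it.
- **15 per cell is an expectation, not a cap.** Power would rise if more women were recruited.

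Two stronger readings are tempting and should not be adopted. Pooling all findings (21 Table 2 entries × 15 = 315 per operator) gives rejection rates of about 24%, 37% and 55% at the three SDs. Hypothesis 2, however, is posed finding by finding, no section specifies a pooled test, and pooling treats several findings on one woman as independent. A reader might also infer that cell size rather than complexity decides which findings reach significance. That is not shown: the easier findings have 15, 15, 45 and 60 intermediate scans and the complex ones 15, 30, 30, 30 and 75, so the ranges overlap. Nor is power negligible throughout: for a 15-point gap, cephalic presentation and amniotic fluid reach 71% and 85%.

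**Conclusion.** The point holds at moderate severity. That one intermediate operator cannot stand for an experience level follows from the protocol alone and rests on no assumption. The size of the error inflation does rest on assumptions: scans as the unit, 85% accuracy, and operator SDs for which the documents give no figure. At the smallest SD and cell it is slight (about 6% against 5%); at the largest it is serious (about 28%). It applies to a claim about experience in general. If the claim is confined to these four operators, operator variation no longer inflates the test, although unassigned case mix could still explain a difference.

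The wording problem is clearest for intrauterine pregnancy and free fluid, where a non-significant result says almost nothing about a 10-point gap. It is weaker, but still present, for cephalic presentation and amniotic fluid.

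**What to change.** Change the wording of sections 4.1.4 and 7.2; no new data are needed.

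1. Report accuracy against the reference standard for each of the four operators, with 95% CIs.
2. Present the intermediate-versus-naïve contrast per finding, and for the easier and complex groups, as an exploratory description of these four operators. Label any CI as conditional on these operators and not as inference about experience level. Without that label, a scan-level CI has the same flaw as the test.
3. For the grouped contrast, allow for several findings coming from the same woman, for example by treating the woman as the cluster.
4. Remove the claim of a significant difference confined to complex findings, and state that p>0.05 will not be taken as no difference.

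Possible text for hypothesis 2: *The observed difference in accuracy between the intermediate operator and the three naïve operators is expected to be larger for complex than for easier findings; it will be described for these four operators only.*

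The cost is that the study gives up a general claim about operator experience. Its design cannot support that claim; it would need several operators at each level.

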### **5. STUDY DESIGN**

This is a prospective observational study in parturients admitted to the emergency department, outpatient department and antenatal care of the PCMH in Freetown, Sierra Leone.

#### **5.1.Population**

##### **5.1.1.Inclusion criteria**

In order to be eligible to participate in the observational study, a patient must meet the following criteria:

- Admitted to the emergency department, outpatient department, in-patient department or antenatal care (ANC) of the PCMH during the study period.
- Fulfills one or more of the five inclusion categories defined in Table 1.
- (Verbal or written) informed consent of the patient or his/her formal representative, if required by ethical committee (decision is pending whether informed consent, either verbal or written, is required from individual patients).

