##### **5.1.2.Exclusion criteria**

The following exclusion criteria will apply in the observational study:

- Ultrasound examination not feasible, e.g., due to electricity breakdown, or physical absence or unavailability of the trained sonographers.

**Table 1.** Inclusion categories as defined by National Protocols and Guidelines for Emergency Obstetric and Newborn care (14) or hospital protocol.

Inclusion criteria	Case Definition
Vaginal bleeding in early pregnancy	Vaginal bleeding or cramping, with amenorrhea or positive pregnancy test <22 weeks of gestation
Pre-eclampsia	Blood pressure $\geq 140/90$ (at least 2 recordings, 4 hours apart) PLUS any of: proteinuria (at least 2+ on dipstick, headache, generalized oedema, visual disturbance).
APH third trimester:	Vaginal bleeding after 22 weeks of pregnancy or in labour before giving birth. May have final diagnosis of abruptio placentae, placenta previa and ruptured uterus.
Prolonged/ Obstructed labour:	Prolonged latent or active phase, cephalopelvic disproportion, obstructed labor, inadequate uterine activity, prolonged expulsive phase.
High risk pregnancy in ANC	Fulfil any of the following criteria (as defined by hospital protocol): 
 
1. Previous Cesarean Section
 
2. Previous still birth
 
3. Age below 18 years
 
4. Short stature (height < 150cm)
 
5. Grand Multipara: Gravida more than 5.
 
6. Fundal Height >40cm
 
7. Suspected breech
 

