#### **6.1.4. Randomization, blinding and treatment allocation**

Patients are prospectively recruited on a consecutive basis. No randomization will be performed. The reference standard operator will be blinded to the results of the ultrasound examinations made with the hand held apparatus and vice-versa.

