#### **7.1.2.Data sharing**

Data derived from this study will be shared with the clinical team directly responsible for patient's care and with hospital leadership and management team for monitoring and/or audit purposes. **Specifically, a copy of the final expert report performed with the conventional apparatus will be attached to the patient's clinical chart to be visualized by the clinical team responsible for patient's care.** After publication of the primary results, on request the pooled dataset will be available for secondary analysis, after judgment and approval of scientific quality and validity of the proposed analysis by the steering committee.

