### **9.2. Recruitment and consent**

No ethical concern is attributable to this study due to its observational nature. No direct therapeutic intervention on patient is part of the study design. Personal information (name, age, community, etc.) from patient chart will be anonymized and no patients will be recognizable during the realization or dissemination phases of the study. Serial obstetrical ultrasound examinations are already standard of care in obstetric patients in PCMH and point of care ultrasound is also normally performed in emergency settings at the outpatient department of the hospital. The report of the expert ultrasound scan would be attached to the clinical chart, as already routine when an ultrasound is performed in the PCMH scanning room. For these reasons, and considering the medical urgency characterizing most inclusion criteria, a waiver of patient individual informed consent is kindly requested to this EC. Sharing of patient data will follow Good Clinical Practice guidelines and ethics review committee advice.

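### The blinding rule does not reach earlier scan reports in the chart, so agreement on the stable findings can be inflated by an unknown amount

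*Protocol*

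**What the plan says.** **Who is eligible.** Section 5.1.1 admits women "Admitted to the emergency department, outpatient department, in-patient department or antenatal care (ANC) of the PCMH during the study period". Section 5 gives a narrower list, "parturients admitted to the emergency department, outpatient department and antenatal care of the PCMH", which leaves out in-patients. The only exclusion, in 5.1.2, is "Ultrasound examination not feasible, e.g., due to electricity breakdown, or physical absence or unavailability of the trained sonographers". Section 5.2 then states: "During a 2-month period all patients meeting the inclusion and exclusion criteria will be recruited". None of these mentions an earlier ultrasound or an earlier enrolment.

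**When the hand-held scan is done.** Section 6.3.2 places it at emergency admission, at the ANC visit or on the ward. The project summary also allows it after admission, when clinically indicated.

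**What may already be in the chart.** Section 9.2 states: "Serial obstetrical ultrasound examinations are already standard of care in obstetric patients in PCMH". It describes attaching the expert report to the chart "as already routine when an ultrasound is performed in the PCMH scanning room". Under 7.1.2 the study adds to this: "a copy of the final expert report performed with the conventional apparatus will be attached to the patient's clinical chart".

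**Who is masked to what.** Section 6.1.4 states: "The reference standard operator will be blinded to the results of the ultrasound examinations made with the hand held apparatus and vice-versa". It does not mention the chart or scans made before enrolment. Masking to clinical information appears only in 7.3, for the offline check of 20 examinations.

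**The concern.** A ward or ANC patient may come to the hand-held scan with a scanning-room report from the same pregnancy already on file. Placenta location, fetal number and dating change little between visits. If both operators have seen that report, their agreement on those items partly reflects a shared source and not two independent readings of images. The primary endpoint is mean accuracy against the conventional scan, so the effect would tend to favour the hand-held device.

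Secondary hypothesis 2 is also exposed. Three of its five complex findings are placenta location, gestational age and multiple pregnancy. A shared report could bring naïve and intermediate operators closer together on exactly those.

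A smaller matter is that nothing limits a woman to one enrolment. Someone scanned in ANC for a previous cesarean section could qualify again in obstructed labour within the two months, with her first expert report in the chart.

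**Working it through.** **The plan's own figure.** The only planned number is 300 patients. It reproduces: 4 operators × 5 categories × 15 = 300, and 5 × 15 = 75 per operator. The protocol gives no share of women with an earlier report and no expected accuracy, so the rest is an illustration.

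**Inputs from the protocol**
- Nine findings are averaged (project summary). I weight them equally.
- Table 2 has 3 + 4 + 4 + 4 + 6 = 21 category-by-finding entries. Placenta location appears in APH and ANC, multiple pregnancy in labour and ANC, and gestational age in pre-eclampsia and ANC. That is 3 of 9 findings and 6 of 21 entries.
- Each category has 4 × 15 = 60 planned women. Each of the three findings is therefore scored in 120 women, 60 of them from ANC.

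**Assumptions**
- q is the share of women whose earlier report exists and is read and followed.
- Agreement is 98% when it is followed.
- True accuracy a is 85% or 75%.
- The other six findings are unaffected.

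**Step 1, one stable finding.** Rise = q × (0.98 − a).

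**Step 2, nine-finding mean.** Rise = (3/9) × q × (0.98 − a).

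Rises in percentage points:

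| q | one finding, a = 85% | nine-finding mean, a = 85% | one finding, a = 75% | nine-finding mean, a = 75% |
|---|---|---|---|---|
| 10% | 1.3 | 0.4 | 2.3 | 0.8 |
| 20% | 2.6 | 0.9 | 4.6 | 1.5 |
| 40% | 5.2 | 1.7 | 9.2 | 3.1 |
| 60% | 7.8 | 2.6 | 13.8 | 4.6 |

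Example: q = 20%, a = 85% gives 0.20 × 0.13 = 0.026 for one finding, and 0.026 / 3 = 0.009 for the mean. If 40% had a report but only half of these were followed, the 20% row applies.

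**Step 3, pooling by entries.** With equal category sizes the factor is 6/21 in place of 3/9. For q from 20% to 60% the rise is 0.7 to 2.2 points (a = 85%) or 1.3 to 3.9 points (a = 75%).

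**Step 4, kappa for one stable finding.** Take 20% prevalence and equal marginals. Chance agreement is 0.2² + 0.8² = 0.68. At a = 0.85, kappa is (0.85 − 0.68)/0.32 = 0.53. At q = 20%, accuracy is 0.876 and kappa is 0.196/0.32 = 0.61. At q = 60%, accuracy is 0.928 and kappa is 0.248/0.32 = 0.78.

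**Step 5, repeat enrolment.** Suppose 10% of 300 examinations were second examinations. There would be 270 distinct women. With within-woman correlation ρ the design effect is 1 + 2 × 0.10 × ρ. For ρ = 0.3 it is 1.06 and the effective n is 283. For ρ = 1 it is 1.20 and the effective n is 250.

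**The case against.** The strongest reply is that few women may have an earlier report. The account of routine scanning in 9.2 is there to support a consent waiver. Section 3.4 points the other way: ultrasound is on hand only some of the time, image quality is often poor, power is unstable, the emergency outpatient department relies on history and examination, and malpresentation and multiple pregnancy are found late. This stands. The two sections are hard to square, and q could lie below every row of the table. It is also a reason to record the share.

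Second, no text says that either operator consults the chart. The expert report is filed for the clinical team, and the hand-held scan is usually done at once with a checklist. A reader might infer that both operators will know the answer; the documents show only that nothing prevents it. If only one of them knew, inflation would not necessarily follow.

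Third, a reader might carry the single-finding rise of 2.6 to 13.8 points over to the primary endpoint. That is not supported. An old report does not settle fetal heart, presentation, amniotic fluid or retroplacental hematoma today, and two of these are among the five complex findings in hypothesis 2.

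Fourth, repeat enrolment is allowed only by silence. Section 7.1 gives each patient a unique code and keeps a logbook, so repeats could be traced. The wording of 6.1.4 might be read to cover an earlier study report. How repeated records are analysed is commonly left to an SAP. This stands, and makes it the lesser part of the point.

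**Conclusion.** The gap is real and belongs to the protocol, since eligibility and reader masking are fixed there and an unrecorded earlier scan cannot be adjusted for afterwards. Followed as written, the plan lets both operators share an earlier report, which can bias the primary accuracy upward. The effect would be uneven: mainly in three stable findings and less in those that change.

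The size is unknown. For 20% to 60% of women with a report that is read and followed, the nine-finding mean would rise by about 0.9 to 2.6 points (true accuracy 85%) or 1.5 to 4.6 points (75%), and by less with a lower share. These figures rest on the assumed 98% agreement, on equal weighting, and on six findings being untouched.

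The documents do not show that agreement is in fact inflated. Nor do they call for confining the primary analysis to women without an earlier scan: once both operators are masked, that restriction is redundant, costs precision and narrows the population.

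**What to change.** - **6.1.4:** extend the rule so that both operators perform and record the study scan without access to earlier ultrasound reports, whether routine or from the study.
- **5.1.1 and 5.1.2:** allow one enrolment per woman, at her first eligible episode. Bring the list of settings in section 5 into line with 5.1.1.
- **CRF:** add one item on whether an ultrasound report from this pregnancy existed or was known to the operator.
- **7.2:** keep all enrolled women in the primary analysis and add a sensitivity analysis by earlier-scan status.

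The cost is slightly fewer records, one more CRF item, and possibly a less favourable accuracy figure. Masking the expert needs some care, because that scan's report also goes into the chart for the clinical team. The rule should therefore apply to performing and recording the study findings.
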